- Sensitivity, specificity, positive and negative predictive value of ^{68}Ga -PSMA-11 PET/MRI for the detection of extra-pelvic nodal metastases, visceral metastases and osseous metastases compared to biopsy and imaging follow-up.

Exploratory

- Sensitivity, specificity, negative and positive predictive value for detection of regional nodal metastases in comparison to cross sectional imaging performed contemporaneously with the ^{68}Ga -PSMA-11 PET/MRI PET.
- One-year PSA progression free survival, comparing patients with and without pelvic nodal metastases.
- Correlation between SUV_{max} from ^{68}Ga -PSMA-11 PET/MRI and short axis diameter of nodal disease on cross sectional imaging correlate to presence of true pathology.
- Incidence of osseous and distant metastatic lesions.

Endpoints

Primary Endpoints

- PSMA-11 PET results for regional nodal disease.
- Nodal histology results from prostatectomy.

Secondary endpoints

- PSMA-11 PET results for extra-pelvic disease.

- Biopsy results and imaging follow-up results

Exploratory Endpoints

- Time to PSA progression
- SUV_{max} of lesions.
- Presence of osseous and distant metastasis.
- Safety: blood pressure, heart rate, self reported adverse events

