- If there was a corresponding positive sclerotic lesion on the CT portion of the ⁶⁸Ga-PSMA-11 PET.

- If there is focal uptake seen on the baseline bone scan performed within one month of ⁶⁸Ga-PSMA-11 PET.

- If there is a lesion noted on the initial MRI performed within one month of ⁶⁸Ga-PSMA-11 PET.

- If within 12 months, follow-up CT demonstrates development of sclerosis.

- If within 12 months, follow-up MRI demonstrates a new bone lesion.

- If within 12 months, follow-up bone scan demonstrates new focal uptake.

(2) False positive:

- If ⁶⁸Ga-PSMA-11 positive bone lesions do not meet the criteria for true positive findings.

iv) Histopathology correlation: for lesions that have biopsy correlation, we will use the following criteria to determine positive and negative lesions:

(1) Positive HP/Biopsy: Confirmed sites of metastatic or tumor involvement by histopathology/biopsy will be discussed with the responsible physician/surgeon.

(2) Negative Biopsy: Patients with suspected tumor recurrence on ⁶⁸Ga-PSMA-11 PET with negative histopathology/biopsy will be handled as outlined below:

(a) Lymph nodes:

- For patients undergoing nodal dissection: Patients will be rescanned with dedicated CT or MRI to determine if the suspicious ⁶⁸Ga-PSMA-11-positive node was removed.

- If ⁶⁸Ga-PSMA-11 positive lymph node is still present, a repeat biopsy can be pursued if clinically feasible and applicable, or follow-up using imaging as described above will be performed.

- If the corresponding node was removed, then this will be considered a False Positive.
- For patients undergoing needle biopsy: Images of the procedure will be reviewed to determine if the correct node was biopsied.
 - If the correct node was biopsied, then a negative biopsy will be considered a False Positive.
 - If the incorrect node was biopsied, then follow-up imaging as described above will be performed.

(b) Bone lesions: Given the high rate of false negative biopsies for osseous metastases in patients with prostate cancer, patients with negative bone biopsies of ^{68}Ga -PSMA-11 PET-positive lesions will be further evaluated:

- If pathology demonstrates an alternative diagnoses that is known to be ^{68}Ga -PSMA-11-positive (eg, renal cell carcinoma (RCC) metastases; Paget's disease), then this will be considered a False Positive.
- If pathology is indeterminate, then follow-up imaging as described above will be performed to determine if the lesion is a True Positive or False Positive.

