(c) Additionally a repeat ^{68}Ga -PSMA-11 can also be obtained, as allowable, in addition to repeat conventional imaging (CT and/or MRI) in cases of negative biopsy to determine if the biopsy was true negative or false negative.

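### Section 10.3.3 iv)(2)(c) permits an optional repeat 68Ga-PSMA-11 scan to help judge a negative biopsy, so the index test can contribute to its own reference standard in the secondary accuracy analysis

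*Combined protocol and SAP*

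**What the plan says.** Section 2.5 sets the secondary objective as the sensitivity, specificity and predictive values of 68Ga-PSMA-11 PET/MRI for "extra-pelvic nodal metastases, visceral metastases and osseous metastases compared to biopsy and imaging follow-up". Biopsy is thus part of the reference standard.

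Section 10.3.3 iv)(2) deals with one situation only, a suspicious PSMA scan with a negative biopsy: "PET with negative histopathology/biopsy will be handled as outlined below". Three items follow.

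- **(a) Nodes.** For needle biopsy: "If the correct node was biopsied, then a negative biopsy will be considered a False Positive". For dissection: "If the corresponding node was removed, then this will be considered a False Positive". If the node is still present or the wrong node was sampled, the plan turns to repeat biopsy or follow-up imaging.
- **(b) Bone.** The plan notes that false negative bone biopsies are common. "If pathology demonstrates an alternative diagnoses that is known to be" PSMA-positive, the finding is a false positive. Where the pathology is unclear, the follow-up imaging criteria decide between true and false positive.
- **(c) All negative biopsies.** A repeat 68Ga-PSMA-11 scan "can also be obtained, as allowable, in addition to repeat conventional imaging (CT and/or MRI"), and its stated purpose is "in cases of negative biopsy to determine if the biopsy was true negative or false negative".

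Item (c) makes no exception for nodes already settled under (a). It gives no criterion for reading the repeat scan and no rule for when that scan disagrees with CT or MRI.

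**The concern.** A reference standard should be independent of the test it is used to assess. Item (c) does more than permit a rescan: its stated purpose is to decide whether the biopsy was right. A second scan with the same tracer is not independent of the first. If uptake in a lesion comes from something other than prostate cancer, a repeat scan may show it again. The plan itself recognises such lesions in (b). Persistent uptake therefore cannot on its own establish that the biopsy missed prostate cancer.

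At stake is the secondary accuracy analysis for extra-pelvic nodes, visceral lesions and bone. Because the rescan is optional and the study calendar in Section 7 does not schedule it, a lesion's classification could also depend on who happened to be rescanned after the scan and the biopsy were known to disagree.

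**Working it through.** The documents give no figure on this point, so there is nothing to reproduce. The check compares the rules and then shows the direction of any effect on assumed counts.

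**Rules side by side**

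1. *Correctly biopsied or removed node, negative pathology.* Item (a) says false positive without qualification. Item (c) applies to negative biopsies generally and asks whether the biopsy was falsely negative. No order of precedence is stated.
2. *Bone, alternative PSMA-positive diagnosis.* Item (b) says false positive. Again, (c) states no exception.
3. *Bone, indeterminate pathology.* Item (b) refers to the follow-up criteria in iii), which use CT, MRI and bone scan. Item (c) adds the PSMA scan.
4. *Visceral lesion with a negative biopsy, or a bone biopsy that is negative but neither indeterminate nor an alternative PSMA-positive diagnosis.* Neither (a) nor (b) covers these, so (c) is the only negative-biopsy rule in iv)(2) that applies.
5. *Criteria i)–iii).* True-positive status rests on size change or PSA response (nodes, visceral lesions) and on CT, MRI or bone scan findings (bone). Repeat PSMA uptake is not listed. Positive lesions that meet no true-positive criterion default to false positive.
6. *Primary endpoint.* For an unresected node, Section 10.3.2 c) uses biopsy or a size-change criterion on imaging. Section 5.3 allows a repeat PSMA scan at the physician's discretion but attaches no classification rule to it.

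Item (c) is therefore the only place where a repeat PSMA scan is given a role in judging the reference result.

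**Direction of effect**

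Take the biopsy at face value, so that a negative biopsy of a PSMA-positive lesion is a false positive (FP). If a share r of these is reclassified as true positive (TP):

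- PPV = (TP + r·FP)/(TP + FP)
- sensitivity = (TP + r·FP)/(TP + r·FP + FN)
- specificity = TN/(TN + (1 − r)·FP)
- NPV = TN/(TN + FN), unchanged

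All counts below are assumed, and every FP is taken to be biopsy-negative.

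| Assumed TP, FP, FN, TN | r | PPV | Sensitivity | Specificity |
|---|---|---|---|---|
| 14, 6, 6, 124 | 0 | 14/20 = 0.70 | 14/20 = 0.70 | 124/130 = 0.954 |
| | 0.5 | 17/20 = 0.85 | 17/23 = 0.739 | 124/127 = 0.976 |
| | 1 | 20/20 = 1.00 | 20/26 = 0.769 | 124/124 = 1.00 |
| 10, 10, 5, 125 | 0 | 10/20 = 0.50 | 10/15 = 0.667 | 125/135 = 0.926 |
| | 0.5 | 15/20 = 0.75 | 15/20 = 0.75 | 125/130 = 0.962 |
| | 1 | 20/20 = 1.00 | 20/25 = 0.80 | 125/125 = 1.00 |

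The one-way movement is built into the formulas. It reflects the fact that iv)(2) applies only to index-positive findings, so PSMA-negative lesions are never re-examined this way. The table shows direction and possible scale. It does not estimate what will happen.

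**The case against.** The strongest reply is that (c) does not classify anything. The scan is optional and comes in addition to CT/MRI, and no sentence says that persistent uptake makes a biopsy falsely negative or a lesion a true positive. Criteria i)–iii) give uptake no route to true positive and default to false positive. On those criteria alone, a biopsy-negative lesion that merely stays avid remains a false positive. Item (c) opens as an addition and can be read as supplementing only the pathways that (a) and (b) leave open. For bone, where the plan regards biopsy as often falsely negative, seeking further evidence is reasonable.

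Much of this stands. A reader might infer that the repeat scan overrules the biopsy. The text permits that outcome but does not require it. A reader might also cite renal cell carcinoma metastases and Paget's disease as lesions that would be wrongly upgraded. Item (b) already makes them false positives when bone pathology shows them, so they show only that uptake is not specific to prostate cancer.

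The objection does not remove the stated purpose in (c). A biopsy found to be falsely negative has no sensible consequence except that the scan was right. Nothing bars the rescan from that judgement, and the narrower reading of (c) is not written down.

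The number of lesions affected may well be small. Section 2.1 describes bone metastases as uncommon at initial staging, and Section 7 schedules a single scan.

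**Conclusion.** The point holds in a limited form. Section 10.3.3 iv)(2)(c) lets the index test contribute to its own reference standard, and it leaves its relation to (2)(a) and to criteria i)–iii) unresolved. Relative to the biopsy at face value, any reclassification it prompts favours the scan.

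The effect is confined to the secondary accuracy analysis. A reader might extend it to the primary endpoint, but the primary rules in 10.3.2 rest on pathology, biopsy and size change and give a repeat PSMA scan no role. Nor do the documents establish that it reaches the exploratory comparisons in 10.3.4, whose confirmation standard is worded as histopathology/biopsy, with conventional imaging follow-up added for PPV.

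The size cannot be computed, because the documents give no expected number of biopsies, negative biopsies or rescans. The PPV values of 70%, 85% and 100% rest on 20 assumed biopsied lesions with six negative, and on the further assumption that uptake alone leads to reclassification. They should not be read as a forecast.

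**What to change.** Amend 10.3.3 iv)(2) as follows.

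- In (c), state that a repeat 68Ga-PSMA-11 scan may be obtained but is not used in any true- or false-positive assignment.
- State that the false-positive rules in (a), and the alternative-diagnosis rule in (b), are final and are not reopened by (c).
- Classify the remaining negative or indeterminate biopsies, including visceral ones, by repeat histology or by the criteria already in i)–iii) that do not rest on PSMA uptake: CT, MRI, bone scan and PSA response, each as stated there.
- Optionally, add a sensitivity analysis that counts every negative biopsy of a PSMA-positive lesion as a false positive.

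This is a change of SAP wording with no new procedure and no change to care. The cost is that PPV may come out slightly lower, and some biopsies that truly missed disease, notably in bone, may stay classed as false positives.

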10.3.4 Analysis of Exploratory Endpoints

PPVs on a per-patient and per-region-basis of ^{68}Ga -PSMA-11 PET for detection of tumor location confirmed by histopathology/biopsy and conventional imaging follow-up will be calculated and reported along with the corresponding two-sided 95% confidence intervals. The paired McNemar's test will be used to compare the PPVs of ^{68}Ga -PSMA-11 PET imaging to the PPVs of conventional imaging.

Sensitivity, specificity, and NPVs on a per-patient basis of ^{68}Ga -PSMA-11 PET for detection of tumor location confirmed by histopathology/biopsy will be summarized in tabular format. Furthermore, the positive and negative likelihood ratios (LR+ and LR-) will be calculated and reported. 95 confidence intervals of sensitivity, specificity, and NPV will be calculated using the Wilson score method. The comparisons of sensitivity, specificity, and NPV on a per-patient basis of ^{68}Ga -PSMA-11 PET imaging will be compared to of sensitivity, specificity, and NPV on a per-patient basis of conventional imaging using a paired McNemar's test.

Detection rates on a per-patient basis of ^{68}Ga -PSMA-11 PET stratified by PSA value (0.2 to < 0.5; 0.5 to < 1.0; 1.0 to < 2.0; 2.0 to < 5.0; ≥ 5.0) will be summarized in tabular format and compared between PSA strata using chi-square analysis. The impact of ^{68}Ga -PSMA-11 PET on clinical management in BCR patients will be evaluated using descriptive statistics.

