10.2 Determination of Sample Size and Accrual Rate

10.2.1 Sample Size and Power Estimate

The estimated sample size will be 200 patients to adequately power the primary aim. The power analysis will be based on the comparison of sensitivity between conventional imaging and PSMA-11 PET. With a power of 80% and a significance level of 0.01, a sample size of 61 patients with nodal metastases is required. The following assumptions are made:

- i. 30% of intermediate to high-risk patients have nodal metastases at prostatectomy.

- ii. 25% of patients will not undergo the planned prostatectomy. Patients that do not undergo prostatectomy will not be included in the analysis population, and will not undergo central imaging review.
- iii. Conventional imaging has a 45% detection sensitivity for nodal metastases on a per-patient basis (2).
- iv. PSMA-11 PET has a 65% detection sensitivity for nodal metastases on a per-patient basis.

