c) Analysis plan for Primary Aim 1: For this study to reach success, 2 out of the 3 readers will have to demonstrate a detection sensitivity of 65% or greater for nodal metastases. Additionally, 2 out of the 3 readers will have to demonstrate a detection specificity of 90% or greater for regional nodal metastases based upon region as defined below on a per patient level. The sensitivity, specificity, positive and negative predictive value of PSMA-11 PET for the detection on a per patient basis will be determined using the below criteria:

- i) True positive patient:
 - (1) PSMA-11 PET-positive for regional nodes; pathology at prostatectomy positive for regional nodes. Region will be defined by the granularity used by the urologist at time of prostatectomy. Sensitivity will be calculated at a patient level by region, meaning that one correct region would make a true positive on a patient level. Only one node needs to correspond between imaging and pathology for a patient to be considered a true positive.
 - (2) PSMA-11 PET-positive for regional nodes; pathology negative for regional nodes; imaging after prostatectomy demonstrates node was not removed at surgery; and follow-up biopsy or imaging demonstrates presence of nodal disease.
 - (a) Criteria for positive node on follow-up imaging: imaging within 3 to 12 months; the node decreases by more than 30% (for patients undergoing systemic treatment or focal therapy at this site); or increase by more than 20% in short axis diameter in the absence of treatment (with a minimum of 3 mm in change in size).
- ii) True negative patient:
 - (1) PSMA-11 PET-negative for regional nodes; pathology at prostatectomy negative for regional nodes.
- iii) False positive patient:
 - (1) PSMA-11 PET-positive for regional nodes; pathology at prostatectomy is negative; and imaging after prostatectomy demonstrates that node is no longer present.
 - (2) PSMA-11 PET positive for regional node, but pathology at prostatectomy is positive for node but in a different nodal region than that node seen on PSMA-11 PET.

iv) False negative patient:

- (1) PSMA-11 PET negative for regional nodes, but pathology at prostatectomy is positive.

v) Non-evaluable:

- (1) PSMA-11 PET positive for regional nodes; pathology negative for regional nodes; imaging after prostatectomy demonstrates node was not removed at surgery; and no definitive follow-up is available.

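### Section 10.3.4 uses a paired McNemar's test to compare PPVs and NPVs, which that test cannot do because each modality has its own denominator

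*Combined protocol and SAP*

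**What the plan says.** Section 2.5 lists as an exploratory objective the "negative and positive predictive value for detection of regional nodal metastases in comparison to cross sectional imaging" done at about the same time as the PET; the synopsis has the same objective.

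Section 10.3.4 gives the analysis. It covers "PPVs on a per-patient and per-region-basis of" the PET, with two-sided 95% confidence intervals, and then states: "The paired McNemar's test will be used to compare the PPVs of" PET and conventional imaging. The next paragraph compares sensitivity, specificity and NPV with those measures "on a per-patient basis of conventional imaging using a paired McNemar's test".

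The section does not say how the paired table is formed for PPV or NPV. The Wilson intervals it mentions are single-proportion intervals and compare nothing. No other section gives a method for comparing predictive values.

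**The concern.** McNemar's test needs each unit to yield a result on both tests within one fixed set. The reference standard supplies such a set for sensitivity (node-positive patients) and for specificity (node-negative patients). It does not for PPV or NPV. A patient positive on PET only belongs to the PET PPV denominator and not to the conventional one, so the denominators are different, partly overlapping groups.

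The analyst would have to choose a table the plan does not define, and the p-value printed beside the PPVs or NPVs would answer a different question. A sensitivity difference could be reported as a PPV difference, a real predictive-value difference could be missed, and the p-value could favour one modality while the observed PPV favours the other. Leaving the table open also allows it to be chosen after the data are seen.

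**Working it through.** **1. The plan's own figure.** The plan gives no figure for the predictive-value comparison. Its only sample-size figure, 61 node-positive patients (section 10.2.1), concerns sensitivity. It reproduces as a one-sample, one-sided calculation: [(2.326×√(0.45×0.55) + 0.842×√(0.65×0.35))/0.20]² = 60.7, rounded up to 61. It does not bear on PPV or NPV.

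**2. The hypotheses differ.** Let p be prevalence, Se sensitivity and FPR the false-positive rate.
- PPV = p·Se / (p·Se + (1−p)·FPR), so equal PPVs means equal Se/FPR.
- NPV = (1−p)(1−FPR) / ((1−p)(1−FPR) + p(1−Se)), so equal NPVs means equal (1−FPR)/(1−Se).
- McNemar on true positives tests equal Se. On correct/incorrect calls it tests equal p·Se + (1−p)(1−FPR). On positivity it tests equal p·Se + (1−p)·FPR.

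None of the McNemar nulls is the PPV or NPV null. Restricting to patients positive on both tests does not help: if one patient-level reference result applies to both, both reads are right or both wrong and no pair is discordant.

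**3. Inputs for an illustration.**
- Analysed: 200 × 0.75 = 150 (section 10.2.1).
- Prevalence: "30% of intermediate to high-risk patients have nodal metastases at prostatectomy".
- Sensitivities: "PSMA-11 PET has a 65% detection sensitivity for nodal metastases on a per-patient basis"; "Conventional imaging has a 45% detection sensitivity for nodal metastases on a per-patient basis".
- PET FPR 0.10, from the success threshold in section 10.3.2(c): "2 out of the 3 readers will have to demonstrate a detection specificity of 90% or greater".
- Assumed, because the documents do not give them: the conventional FPR; the dependence between reads given disease status, from independent to a joint positive probability halfway between independence and its maximum; and a two-sided 5% level.

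PET: PPV = 0.195/(0.195 + 0.070) = 0.736; NPV = 0.630/(0.630 + 0.105) = 0.857.

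**4. Three conventional FPRs, each solved to equalise one quantity.**

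| Case | Conventional FPR | PPV, PET vs conventional | NPV, PET vs conventional |
|---|---|---|---|
| 1. Equal PPV | 0.10×0.45/0.65 = 0.0692 | 0.736 vs 0.736 | 0.857 vs 0.798 |
| 2. Equal accuracy | 0.10 − 0.06/0.70 = 0.0143 | 0.736 vs 0.931 | 0.857 vs 0.807 |
| 3. Equal positivity | 0.10 + 0.06/0.70 = 0.1857 | 0.736 vs 0.509 | 0.857 vs 0.776 |

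Here 0.06 = 0.30 × (0.65 − 0.45).

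Case 1 denominators: PET-positive 150×0.265 = 39.8; conventional-positive 150×0.1835 = 27.5. Positive on both: 150×(0.30×0.65×0.45 + 0.70×0.10×0.0692) = 13.9 if independent, 20.7 at half-maximum dependence.

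**5. Rejection rates.** 100,000 simulated trials per case; each range runs from independent reads to half-maximum dependence. The comparator is the weighted generalised score test, (PPV₁−PPV₂)² / {[m(1−m) − 2C](1/n₁+1/n₂)}. Here n₁ and n₂ are the numbers of positives, m is the pooled PPV, and C = [TP_both(1−m)² + FP_both·m²]/(n₁+n₂). The NPV version is analogous.

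| Case | McNemar, true positives | McNemar, correct/incorrect | McNemar, positivity | Score test, PPV | Score test, NPV |
|---|---|---|---|---|---|
| 1 | 39–55% | 12–15% | 44–61% | 5% | 40–55% |
| 2 | 39–55% | 3% | 85–95% | 53–61% | 31–42% |
| 3 | 39–55% | 70–86% | 3–4% | 70–87% | 62–79% |

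These use exact McNemar; the asymptotic form gives 48–64%, 15–21% and 50–71% in case 1. In case 2 the true-positive table is significant for PET while the observed PPV favours conventional imaging in 38–54% of trials.

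**6. Limit for NPV.** With conventional sensitivity 45%, its NPV cannot exceed 0.70/(0.70 + 0.165) = 0.809, below PET's 0.857. False rejection of equal NPVs therefore cannot arise at these sensitivities and is not claimed.

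**The case against.** The strongest points on the other side are these.

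- **The scenarios are tuned.** Each conventional FPR was solved to equalise one quantity, so the rates show what can happen, not what to expect. That stands. The true-positive table is simply the sensitivity test, and the plan does not say it would be used for PPV; but it does not say which table would be used at all.
- **The 5% level is a choice.** Section 10.3.4 states no test level, and the only one in the plan is 0.01. At 0.01, case 1 rejects in 18–28% (true positives), 5% or less (correct/incorrect) and 22–37% (positivity). The opposite-direction result in case 2 falls to 17–28%. The rates shrink; the fault remains.
- **Section 10.3.2(c) complicates the labels.** Its region matching could give two positive reads different labels, so the both-positive table need not be fully concordant. Even then it drops every patient positive on one test only, about 26 to 39 patients in case 1, so it still does not compare the PPVs. Region mismatches counted as false positives would also lower PET's PPV: to 0.71, 0.67 or 0.61 if 10%, 25% or 50% of the node-positive patients who are not true positives were classed that way (assumed shares).
- **The same rules let the PET result move patients between the sensitivity and specificity denominators.** This is a fair warning. McNemar suits those two measures only if the reference sets are fixed independently of either modality. Section 10.3.4 refers to confirmation by histopathology or biopsy for these measures, which allows that.
- **The comparison is exploratory**, and reporting estimates with intervals and no p-values would also avoid the error. True, but the plan commits to the tests.

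**Conclusion.** The concern holds. As written, section 10.3.4 names a test that cannot test equality of PPVs or NPVs, and no other section supplies one that can. This follows from the definitions and needs no assumption about accuracy. The size does depend on assumptions. At the plan's sensitivities and prevalence, PET specificity 90%, a 5% level and the assumed conventional FPRs and dependence, McNemar rejects equal PPVs in 12% to 61% of trials depending on the table. It also finds 3–4% where the score test finds real PPV differences in 53–87% of trials. The consequence is confined to exploratory p-values and per-region intervals. The success rule in section 10.3.2(c), the sample size and the point estimates are unaffected. It should be corrected before analysis.

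**What to change.** Amend section 10.3.4 as follows.

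- **Sensitivity and specificity:** keep McNemar's test, per patient, within node-positive and node-negative sets fixed by the reference standard and identical for both modalities. State that reference explicitly, since the patient classification in section 10.3.2(c) depends partly on the PET result.
- **PPV and NPV:** replace McNemar's test with one pre-specified method for paired predictive values. Options are the weighted generalised score test; a GEE of confirmed status on test type among positive (or negative) reads, clustered by patient; or a patient-level bootstrap of the difference.
- **Per-region PPV:** define the regions, and use patient-clustered variance for intervals and comparisons. Under either use of the term in the plan (pelvic nodal regions in section 10.3.2; extra-pelvic nodal, visceral and osseous sites in section 10.3.3) one patient can contribute several.

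The cost is a short text edit and a little more analysis code, with no additional patients or scans. Per-region intervals may widen.

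### The PET-versus-conventional comparison is planned and sized for regional nodal metastases, but section 10.3.4 analyses it for an undefined tumor location, with no stated population and no single reference for both tests

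*Combined protocol and SAP*

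**What the plan says.** The synopsis and section 2.5 list as an exploratory objective the sensitivity, specificity, "negative and positive predictive value for detection of regional nodal metastases in comparison to cross sectional imaging performed contemporaneously with the" PSMA-11 scan. Section 10.2.1 makes this contrast the basis of the sample size: "The power analysis will be based on the comparison of sensitivity between conventional imaging and PSMA-11 PET". Its inputs are nodal throughout: "Conventional imaging has a 45% detection sensitivity for nodal metastases on a per-patient basis", "PSMA-11 PET has a 65% detection sensitivity for nodal metastases on a per-patient basis" and "30% of intermediate to high-risk patients have nodal metastases at prostatectomy". The result is stated as "With a power of 80% and a significance level of 0.01, a sample size of 61 patients with nodal metastases is required".

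Section 10.3.4 is the only place that describes an analysis of PET against conventional imaging. It takes per-patient sensitivity, specificity and NPV of "PET for detection of tumor location confirmed by histopathology/biopsy will be summarized in tabular format", and compares them with conventional imaging by a paired McNemar test. The PPV in the same section has a wider reference, which adds conventional imaging follow-up. The section does not define tumor location and names no analysis population. It also contains PSA strata that start at 0.2 and an assessment of management in BCR patients. Neither fits newly diagnosed men awaiting prostatectomy.

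Three other places matter:

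- Section 10.3.1 restricts the analysis to operated men with histology, but only for the primary endpoint.
- Section 10.3.2 c) gives patient categories for PSMA-11 PET alone. Regions are matched to pathology, so that "one correct region would make a true positive on a patient level". Under i(2), a pathology-negative man becomes a true positive if a PET-positive node was left in place and follow-up biopsy or imaging shows disease.
- Section 5.3, Clinical Follow-up b, sends men with PET-positive osseous or distant lesions to further imaging or targeted biopsy.

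**The concern.** A paired comparison of two tests needs one target, one population and one reference that does not depend on either test. Sections 2.5 and 10.2.1 supply the target. Section 10.3.4, where the test is specified, changes it and leaves the other two open.

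Two things are at stake. First, an analyst who follows 10.3.4 as written need not produce the nodal contrast on which the trial was sized, and no other section produces it. Second, each way of filling the gap from elsewhere in the plan (distant biopsies under 5.3 b, or the follow-up rule in 10.3.2 c) brings in disease-positive men who were verified because PET was positive. CT/MRI has no matching route, so the comparison leans towards PET for reasons unrelated to nodal accuracy.

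**Working it through.** **1. The plan's own figure.** Inputs from 10.2.1: 45%, 65%, 80% power, significance level 0.01. A one-sample normal approximation at one-sided 0.01 gives

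n = [(2.3263 × √(0.45 × 0.55) + 0.8416 × √(0.65 × 0.35)) / 0.20]² = 60.7, rounded up to 61.

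The stated 61 is therefore reproduced as a calculation on nodal sensitivity, which confirms the target that the sizing had in mind. (The sidedness is inferred; the plan does not state it.)

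**2. Expected numbers.** From 10.2.1: 200 × 0.75 = 150 operated men; 150 × 0.30 = 45 node-positive; 105 node-negative. That 45 is below 61, and that a one-sample formula is paired with a McNemar test, are separate matters and are not needed here.

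**3. The definitions side by side.**

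| | 2.5 / 10.2.1 | 10.3.2 c) | 10.3.4 sens., spec., NPV | 10.3.4 PPV |
|---|---|---|---|---|
| Target | Regional nodal (2.5); nodal (10.2.1) | Regional nodal | Tumor location, undefined | Tumor location, undefined |
| Reference | Prevalence taken at prostatectomy | Region-matched pathology, plus follow-up of retained PET-positive nodes | Histopathology/biopsy | Histopathology/biopsy and imaging follow-up |
| Scoring rule for CT/MRI | None given | None | None | None |

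**4. Direction of the effect.** Suppose k operated men with negative nodal pathology enter the disease-positive group because a positive PET led to verification. The route may be a biopsied distant site (literal 10.3.4) or a retained node confirmed on follow-up (10.3.2 c) i(2)). PET is positive in all k by construction. In the McNemar table for sensitivity, each such man either adds a pair in PET's favour (CT/MRI negative) or changes nothing (CT/MRI positive). None can add a pair in favour of CT/MRI.

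**5. Size, on assumed counts.** The documents give no such split. Take 29 of 45 detected by PET (64.4%) and 20 of 45 by CT/MRI (44.4%), the nearest whole numbers to 65% and 45%. If CT/MRI missed all k men:

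| k | PET | CT/MRI | Difference = (9 + k)/(45 + k) |
|---|---|---|---|
| 0 | 29/45 = 64.4% | 20/45 = 44.4% | 9/45 = 20.0% |
| 1 | 30/46 = 65.2% | 20/46 = 43.5% | 10/46 = 21.7% |
| 4 | 33/49 = 67.3% | 20/49 = 40.8% | 13/49 = 26.5% |

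If CT/MRI was also positive in all k, the difference is 9/(45 + k): 19.6% at k = 1 and 18.4% at k = 4, and the McNemar pairs are unchanged. The range at k = 4 is thus 18.4 to 26.5 points, with nodal performance at prostatectomy the same throughout.

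**6. PET figures alone.** Assume also that 11 of the 105 pathology-negative men are PET-positive. Pathology only gives a specificity of 94/105 = 89.5%. If one of the 11 has a retained node confirmed on follow-up imaging, 10.3.2 c) gives 94/104 = 90.4%, and sensitivity moves from 64.4% to 65.2%. The two definitions give different per-patient figures on the same men, so each needs its own label.

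**The case against.** The best defence is that the term is loose rather than wrong. Section 10.3.4 serves the exploratory objectives, and the relevant one names regional nodal metastases, so a sensible analyst would read tumor location as pelvic nodes. Pathology as reference agrees with 10.2.1, which speaks of disease at prostatectomy. This is fair, and on that reading the target is restored. It does not supply a population, a scoring rule for CT/MRI or one reference for all four measures. The recurrence-setting text in the same section also makes the benign reading less safe.

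Section 10.3.3 iv(2)(a) offers a partial answer on reference. After a nodal dissection with negative pathology, a removed node is a false positive and a retained node goes to repeat biopsy or follow-up imaging. So a reader should not infer that 10.3.4 must score every retained node as a false positive. But 10.3.4 does not refer to that rule, and the rule also starts from a PET-positive node.

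Three stronger readings are not supported:

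- *That specificity cannot be estimated because every man has biopsy-proven cancer.* Sections 5.3 and 10.3.2 limit the reads to pelvic nodes, bone and soft tissue outside the pelvis. The primary tumour is never scored.
- *That unoperated men with distant disease will inflate PET sensitivity.* Item ii of 10.2.1 takes them out of the analysis population and out of central imaging review. The restriction should be repeated in 10.3.4, but no inflation from this source can be claimed.
- *That PET could pass in 10.3.2 and fail in 10.3.4.* The 65% and 90% thresholds belong to 10.3.2 c), by reader and for two of three readers. Section 10.3.4 has no threshold.

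**Conclusion.** The point holds as a mismatch between the comparison that was planned and sized and the analysis that is written for it. As worded, 10.3.4 is not confined to regional nodes or to operated men and uses two references. Both readings open to the analyst can admit positives verified only through PET. The McNemar comparison of sensitivity can then move only in PET's favour. On assumed counts, four such men shift a 20.0-point difference to between 18.4 and 26.5 points, depending on whether CT/MRI also saw them.

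This rests on 5.3 b and 10.3.2 c) i(2) being the only verification routes of this kind that the plan writes down, and on splits that the documents do not give. The comparison is labelled exploratory and does not enter the primary success rule. The consequence is a sizing contrast without a usable analysis and two sets of PET figures that could be confused. The trial's success criterion does not change.

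**What to change.** In section 10.3.4:

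- Replace tumor location with regional nodal metastases.
- Restrict the per-patient comparison of PET with conventional imaging to the operated population of 10.3.1.
- Use nodal pathology at prostatectomy as the one reference for both tests, without the follow-up rule of 10.3.2 c) i(2).
- Score both tests at the same level: region-matched where the existing CT/MRI reads allow it, otherwise patient-level positive or negative for both.
- Label the resulting PET figures as pathology-only and distinct from the composite result of 10.3.2 c). The two will still differ; the label and the common reference are what the change provides.

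The stated 61 is unaffected. The cost is SAP wording, one table, and scoring of the existing CT/MRI results for pelvic nodes. Inclusion requires that a diagnostic CT or MRI within 90 days exists, but the plan defines regional reads for PET only. If the existing reports do not give nodal results by region, the patient-level option applies. The pathology-only PET figures may be slightly less favourable than the composite ones.
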